### **1.1 Purpose of the study**

Frailty, an aging-related clinical syndrome associated with low physiologic reserve, is a significant problem for older survivors of cancer. Frailty can be characterized by a combination of symptoms, such as low energy, weakness, slower walking speed, reduced participation in activities, and weight loss to calculate a score based on Fried's frailty criteria. Our group has shown that older survivors of cancer (aged 65+) are at a 46% greater risk of being frail than those without cancer. For older adults with cancer receiving standard of care (surgery with or without chemotherapy), frailty predicts surgical complications, chemotherapy intolerance, and mortality. Unfortunately, no effective treatments for frailty in older survivors of cancer exist. Recently, the National Cancer Institute (NCI) convened a panel of experts for a Think Tank on “Cancer-Related Accelerated Aging” and resolved that trials for frailty in older survivors of cancer are urgently needed.

Inflammation is a major contributor to frailty and a predictor of post-treatment frailty in patients with cancer. Due to the strong association between inflammation and frailty, interventions aimed at reducing inflammation may ultimately reduce frailty and improve post-treatment outcomes for older adults with cancer. Dietary supplements such as epigallocatechin-3-gallate (EGCG) with known anti-inflammatory properties might serve as a practical approach to circumvent chemotherapy-induced frailty in older cancer survivors.

Frailty disproportionately affects African Americans/Blacks (AA/B) who also bear the highest cancer burden. AA/B have a four-fold increased odds of being frail compared to Whites and factors underlying this racial disparity in frailty are unknown. However, research shows that AA/B have elevated inflammatory markers which suggests that inflammation might contribute to the increased risk of frailty. Given the fact that older AA/B with cancer are underrepresented in clinical trials and are at the highest risk of frailty, it is imperative that trials are specifically designed to include this underrepresented group.

This is a two-arm phase 2, single site randomized controlled trial (RCT), oversampling for AA/B, to obtain preliminary data on the feasibility of a 12-week daily EGCG supplementation and on the

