***Epigallocatechin-3-gallate (EGCG) is a promising intervention for frailty.*** Numerous studies are evaluating non-steroidal anti-inflammatory drugs to treat cancer-related toxicities but its long-term use is contraindicated in older adults. Thus, anti-inflammatory agents with low toxicity risk to treat frailty in older survivors of cancer are needed. EGCG is a tolerable anti-inflammatory dietary supplement and is associated with reduced functional decline in older adults. EGCG supplementation reduces TNF- $\alpha$  related immune responses, including levels of TNF- $\alpha$ , IL-6, and IL-1 $\beta$ . A completed Phase 2 trial using 800mg EGCG in patients with prior advanced colon adenoma or colon cancer, found that EGCG at this dose was safe, had low toxicity risk, and was well tolerated. The bioavailability of EGCG is both dose and pH dependent and pharmacokinetic studies showed that the daily supplementation of 800mg EGCG results in the highest serum concentration of EGCG and this is further enhanced by the simultaneous intake of 250mg ascorbic acid (vitamin C; VitC). In addition, intervention studies showed that 12-week oral supplementation of EGCG improved outcomes, such as weight loss in adults with obesity. These data suggest that 800mg EGCG plus 250mg VitC taken for 12 weeks may be safe and efficacious in reducing inflammation and frailty in older survivors of cancer. Our proposed trial will be the first of its kind.

***Addressing racial disparities in frailty in older adults with cancer is critical.*** Despite the fact that African Americans/Blacks (AA/B) bear the greatest burden of frailty and cancer, they are

[figure not shown]
underrepresented in oncology clinical trials and the causes of the racial disparity in frailty is unknown. Furthermore, AA/B account for 9% of the population of adults aged 65+ and this number is expected to increase to 13% by 2060. It has also been shown that AA/B have elevated inflammatory markers including CRP and IL-6 compared to Whites, which suggests that inflammation might play a role in the racial disparity of frailty. It is imperative that trials for older cancer survivors are designed to include AA/B, thus guide the development of health equitable interventions.

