***Exploratory Aims:***

- 1) To explore if there are racial (AA/B vs White) or treatment differences in the effects of EGCG on frailty and TNF- $\alpha$  related immune responses.
- 2) To obtain preliminary data on the effects of a 12 week oral EGCG supplementation compared to usual care on patient reported outcomes (symptom burden as measured by the MD Anderson Symptom Inventory (MDASI) and quality of life as measured by the Functional Assessment of Cancer Therapy – Colon Cancer (FACT-C) or FACT-General) and physical function (measured by Timed up and Go (TUG), Short Physical Performance Battery (SPPB), and Yale Physical Activity Survey).
- 3) To explore transcriptomic and epigenetic differences (using isolated PBMCs) between older pre-frail and frail cancer survivors.
- 4) To perform qualitative analysis in order to gain insights into the frailty experience of older cancer survivors. (post-adjuvant treatment).

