#### **4.4 Registration**

For subjects who are eligible and who provide written informed consent or verbal consent, the following information will be entered into a master list using either Research Electronic Data Capture (REDCap) or another secure electronic database (e.g., password-protected Excel database on a password-protected networked drive). This information is needed to contact subjects during the study to troubleshoot any issues, remind them of study appointments, etc.:

- Subject ID number (used to identify the subject on all study forms and lab specimens)
- Subject name
- Subject phone number
- Subject email address
- Subject address of residence including nine-digit zip code
- Birth date (MM/DD/YYYY)
- Gender
- Race
- Cancer primary site
- Documentation of cancer stage, surgery, and completed cancer treatment regimen
- Most recent IRB approval date
- Name of person registering study subject
- Eligibility verification (FFS)

- Treatment facility
- All the information listed above in the Screening Log (*Section 4.2*)

---

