## **5.6 Randomization**

Randomization will be revealed to the subject at the end of the baseline assessment and immediately before delivering the study drug.

We will employ two arms in a 1:1 allocation ratio:

1. EGCG: 12 weeks daily of 800mg EGCG +250mg VitC taken 1 time a day at breakfast (four 200mg EGCG capsules will be packaged with one 250mg VitC tablet)
2. Usual care

Consented subjects will be randomized with a computer-generated random numbers table with block sizes of 2. We will stratify by race (Black vs other) and treatment type (surgery vs other).

The random numbers tables will be generated centrally using software provided by [name], the project biostatistician. A total enrollment of 40 subjects is planned. Due to the study design the PI, study subjects, personnel, and statisticians will be un-blinded to the treatment assignments.

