### 11.1 Sample size determination

We plan to enroll 40 subjects (20;  $\geq 6$  AA/B per arm). Evaluation of recruitment and adherence to the intervention is required for planned future Phase 2/3 frailty trials in older cancer survivors.

*Aim 1:* With a feasibility target of 70% of

Protocol Date: January 2016

44

randomized subjects completing the study we expect at least 14 evaluable patients per arm, which is appropriate for small randomized studies and it will allow us to obtain preliminary estimates of descriptive statistics (mean, standard deviation (SD), and confidence intervals (CI)). *Aim 2:* At significance level  $\alpha=0.15$ ,  $N=14$  per arm will provide 70% power to detect effect size (standardized mean change in frailty score) of 0.66, if pre-post correlation=0.5 (conservative estimate for FFS; Figure 5).

**Analyses:** *Aim 1:* For each feasibility outcome (recruitment and adherence), we will evaluate proportions of subjects meeting criterion and report percentages with CIs. For AEs, we will report the total and severity of AE's per group. *Aim 2:* Descriptive statistics will be calculated at baseline, post-intervention, and for pre-post change scores for subjects in EGCG and UC arms. To evaluate the preliminary efficacy estimates of EGCG on FFS we will use an analysis of covariance (ANCOVA) model (outcome=FFS at post, covariates: FFS at baseline and arm). Estimates of distribution characteristics (e.g., mean, variance, pre-post correlation) and preliminary estimates of efficacy will inform the design and sample size of our planned future study. *Aim 3:* Similar analyses to Aim 2 will be performed for TNF- $\alpha$ , TNFRI, TNFRII, IL-6, IL-1 $\beta$ , and CRP. If data for inflammatory markers are missing due to lower limit of detection, we will use appropriate imputation methods. *Aim 4:* Using similar analyses to Aim 2, we will conduct preliminary subgroup analyses by race and treatment type.

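### Randomization is stratified by race and treatment type, but the Aim 2 and Aim 3 models leave both factors out; adding them is a minor, low-cost refinement

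*Combined protocol and SAP*

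**What the plan says.** Section 5.6 (Randomization) allocates 40 subjects 1:1 in blocks of 2 and states "We will stratify by race (Black vs other) and treatment type (surgery vs other").

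Section 11.1, under Analyses, gives the Aim 2 model for the Fried Frailty Score (FFS) as "outcome=FFS at post, covariates: FFS at baseline and arm". For the inflammatory markers it says "Similar analyses to Aim 2 will be performed for" TNF-α and five further markers.

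The two factors come back only as subgroup variables. Section 11.1 says "we will conduct preliminary subgroup analyses by race and treatment type", and the first exploratory aim reads "To explore if there are racial (AA/B vs White) or treatment differences in the effects of EGCG on frailty" and immune responses. Section 11.2 (Statistical analysis) neither adds the strata to the models nor says why they are left out.

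**The concern.** Stratifying balances a factor across the arms. If that factor also predicts the outcome, the treatment estimate becomes less variable, but the analysis recognizes this only when the factor is in the model. Otherwise the factor's variance stays in the error term, the reported standard error overstates the true one, and the test rejects less often than its nominal level.

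The protocol itself presents race as related to the outcomes. Section 1.1 says "AA/B have a four-fold increased odds of being frail compared to Whites", and Section 1.2 says "AA/B have elevated inflammatory markers including CRP and IL-6 compared to Whites". What matters for the model is narrower: whether race or treatment type predicts the week-13 value once the baseline value is known.

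At stake are the Aim 2 and Aim 3 treatment-effect estimates, their intervals and their tests. The mean, variance and pre-post correlation that Section 11.1 also passes to the next trial are not affected.

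**Working it through.** **Inputs from the documents.** 40 randomized 1:1 in blocks of 2 within four strata (Section 5.6); 12 of 40 Black (Section 3 enrollment table); 14 evaluable per arm, effect size 0.66, pre-post correlation 0.5 and 70% power (Section 11.1); two-sided α = 0.15 and complete-case analysis (Section 11.2).

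**Assumptions.** Normal outcomes (FFS is a 0–5 score, so results are approximate); loss at random; 40% of patients treated by surgery only. Power did not change materially with a surgery share of 20% or 60%. R² below is the share of the variance left after baseline that the strata explain. The documents give no value for it.

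**Step 1: the plan's own figure.** Residual SD = √(1 − 0.5²) = 0.866. Noncentrality = 0.66 / (0.866 × √(2/14)) = 0.66 / 0.327 = 2.016. With df = 28 − 3 = 25 and two-sided α = 0.15, power is 70.4%. The stated 70% is right for the model as written.

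**Step 2: two added covariates, by formula.** df falls to 23. With R² = 0, power is 70.3%. With R² = 0.04, the residual SD is √(0.75 × 0.96) = 0.849 and power is 71.6%. These are upper bounds because they assume the strata stay perfectly balanced after dropout.

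**Step 3: simulation with dropout.** 100,000 trials per setting, stratified blocks of 2, 12 of 40 lost at random. Monte Carlo error is about 0.11 point for type I error and 0.15 point for power. Differences are taken before rounding, so they can differ by 0.1 from the rounded columns.

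| R² of strata given baseline | Type I, planned / adjusted | Power, planned / adjusted | Change (points) |
|---|---|---|---|
| 0 | 0.151 / 0.150 | 68.5% / 67.2% | −1.3 |
| 0.03 (race only) | 0.146 / 0.151 | 68.9% / 68.6% | −0.3 |
| 0.04 (race only) | 0.146 / 0.150 | 68.7% / 68.7% | 0.0 |
| 0.05 (race only) | 0.144 / 0.151 | 69.0% / 69.3% | +0.3 |
| 0.10 (split between factors) | 0.137 / 0.151 | 68.9% / 71.0% | +2.1 |
| 0.20 (split between factors) | 0.123 / 0.148 | 69.6% / 75.1% | +5.6 |

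Mean standard errors (planned / adjusted) are 0.333 / 0.338 at R² = 0 and 0.333 / 0.331 at R² = 0.04. Allowing for the slightly larger t quantile at 23 df (1.489 against 1.485), the 85% interval widens by 1.8% at R² = 0 and narrows by 0.3% at R² = 0.04. Break-even is therefore at about R² = 0.04.

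**Step 4: what R² might race have?** Convert the four-fold odds to a standardized difference: ln(4) × √3 / π = 0.764. Assume the same gap at both visits, a within-race SD of 1, and 30% Black (variance 0.3 × 0.7 = 0.21).

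- The gap remaining at week 13 given baseline, with within-race correlation 0.5, is 0.764 × (1 − 0.5) = 0.382.
- The variance of race given baseline is 0.21 / (1 + 0.21 × 0.764²) = 0.187.
- The explained variance is 0.382² × 0.187 = 0.0273.
- Partial R² = 0.0273 / (0.75 + 0.0273) = 0.035.

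Reading 0.5 as the overall rather than the within-race correlation gives 0.041. A within-race correlation of 0.3 gives 0.056, where power moves from 61.9% to 62.6%. A correlation of 0.7 gives 0.019, where power moves from 81.6% to 80.9%. Over that range, adjusting changes power by −0.7 to +0.8 point.

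No such derivation is possible for the markers, because Section 1.2 says only that they are elevated. Nothing in the documents shows that treatment type predicts the week-13 value given baseline.

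**The case against.** The strongest case against is that no benefit is demonstrated for this trial. At the one R² the documents suggest, adjusting leaves power unchanged, and there are reasons to think the true value is lower:

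- Section 11.1 calls the correlation of 0.5 conservative. A higher correlation leaves less for race to explain.
- Section 3.3 admits only patients with FFS of 2 or more. Suppose 0.5 is the correlation within that selected group, and the group is the top 15–35% of the frailty distribution (an assumed range). The same model then needs an underlying correlation of about 0.7–0.8, and race's partial R² falls to about 0.01–0.02. At R² = 0.02 power goes from 68.7% to 68.0%, a loss of 0.7 point.
- The odds ratio compares Black with White people on being frail. The stratum is Black vs other, among patients already selected for frailty.

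A further argument is that the planned model is valid, simple and the one the power calculation matches, so the adjusted model should be at most a sensitivity analysis.

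Most of this stands. It rules out presenting the change as a power gain, and it shows that a loss of up to about 1 point is as plausible as a gain. It does not make the adjustment unsound. The case for it is that the analysis would follow the design, the type I error would stay near the stated 0.15 whatever the strata explain, and the covariates would be fixed in advance. The last point has some weight here, because Section 5.6 leaves the investigator and statisticians unblinded and Section 11.2 leaves later model changes loosely defined.

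**Conclusion.** The mismatch is real and its consequence is small and in the safe direction. The planned model is unbiased, does not inflate false positives, and supports the stated 70% power. Its only weakness is conditional: if race or treatment type predicts outcome beyond baseline, its intervals are slightly too wide and its test mildly conservative (type I error 0.146 at R² = 0.04).

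Adjusting changes power by −1.3 points if the strata are not prognostic and by about zero near R² = 0.04. The gains at R² = 0.10 and 0.20 are illustrative, since the documents support neither value. All figures assume 28 evaluable patients, loss at random and approximately normal outcomes. This is a refinement worth considering, not a correction of an error.

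**What to change.** In Section 11.1, specify the Aim 2 model as FFS at post-intervention on baseline FFS, arm, race stratum (Black vs other) and treatment stratum (surgery vs other), using the strata as randomized. Enter the strata as two main effects only: with 28 evaluable patients, about 8 of them Black (12 × 0.7 = 8.4), four-cell or interaction terms would be too much. Add the same two covariates to the Aim 3 marker models. Name this the main analysis and keep the baseline-plus-arm model as a labelled sensitivity analysis. If the team prefers the simpler model, one sentence giving the reason would close the point.

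The cost is one line of text. No new data are needed: Section 4.4 already records race and "Documentation of cancer stage, surgery, and completed cancer treatment regimen" at registration. The sample size is unchanged. The downside is two degrees of freedom and about 1 point of power if neither factor is prognostic given baseline.

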**Summary.** Cancer treatment induced frailty is a significant burden to survivors of cancer. Safe and feasible interventions to reduce frailty in this population will be beneficial. Even though many trials have investigated the anti-tumor and cancer preventive properties of EGCG, none have investigated the role of this polyphenol in reducing frailty in older cancer survivors who have completed surgery with or without chemotherapy. This study serves as a feasibility trial of an EGCG intervention and to obtain preliminary data on the effect of EGCG on reducing inflammation and improving frailty, physical function, symptom burden, and quality of life and whether these effects differ by race.

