#### **1.4 Application of pilot data and background data to proposed study**

Based on the literature and our preliminary data we propose the following model by which EGCG circumvents chemotherapy related inflammation, leading to a reduction in frailty and symptoms as well as an improvement in physical function and quality of life. The combined insult of cancer,

surgery, and adjuvant chemotherapy results in a heightened inflammatory state characterized by elevated pro-inflammatory molecules, increased circulating immune cells, and disruption in the homeostasis of the ratios of immune cells. Prolonged exposure to this inflammatory state may cause insults to a variety of organ systems that ultimately manifest as frailty. This frail state can then lead to increased symptoms, decreased quality of life, and decreased physical performance.

**Theoretical Framework:** EGCG is a promising intervention for frailty but has not been systematically studied. We will determine the safety, feasibility, and efficacy for EGCG on reducing frailty and TNF- $\alpha$  related immune responses in older cancer survivors and explore whether there are any differences by race and treatment type in the efficacy of this intervention. We will also explore the effect of EGCG on physical performance, symptoms, and quality of life. We hypothesize that EGCG is safe and will improve frailty in older cancer survivors by reducing TNF- $\alpha$  related immune responses (as measured by serum levels of TNF- $\alpha$ , TNFRI, TNFRII, IL-6, IL-1 $\beta$ , and CRP) and circulating immune cells (as measured by lymphocytes, monocytes, neutrophils, total WBC, NLR, LMR) (Figure 4).

**Figure 4:** Theoretical Model

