### **2.3 Study Outcomes**

***Aim 1:*** To determine the feasibility and safety of conducting a two arm RCT as measured by recruitment rate, adherence to study procedures and EGCG intervention, and adverse events.

***Aim 2:*** To obtain preliminary data on the effects of EGCG vs UC on frailty measured by FFS (weight loss, weakness measured by hand-grip dynamometry, slowness measured by 4 meter walk test, physical activity measured by the GODIN Leisure-Time Physical Activity, and exhaustion

measured by the symptom inventory) and the Deficit Accumulation Frailty Index (DAFI) based on the geriatric assessment.

**Aim 3:** To obtain preliminary data on the effects of EGCG vs UC on TNF- $\alpha$  related immune responses (measured by serum levels of TNF- $\alpha$ , TNFR I, TNFRII, IL-6, IL-1 $\beta$ , and CRP) and circulating immune cells as measured by lymphocytes, monocytes, neutrophils, total WBC, NLR, LMR in older survivors of CC.

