Not Applicable (N/A); Geriatric Assessment (GA); Aim 1 (A1); Aim 2 (A2); Aim 3 (A3); Exploratory Aim 1 (EA1); Exploratory Aim 2 (EA2); Exploratory Aim 3 (EA3); Exploratory Aim 1 (EA4)					

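### Exploratory Aim 1 asks whether EGCG's effect differs by race or treatment type, but the plan analyses subgroups and never specifies the difference between their effects or its confidence interval

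*Combined protocol and SAP*

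**What the plan says.** The question appears in three places. Among the exploratory aims in section 2.3 it is "To explore if there are racial (AA/B vs White) or treatment differences in the effects of EGCG" on frailty and TNF-alpha related immune responses. The theoretical framework in section 1.4 says the trial will "explore whether there are any differences by race and treatment type in the efficacy of this intervention". The summary closing section 1.2 asks "whether these effects differ by race".

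The analysis is one sentence in section 11.1: "Using similar analyses to Aim 2, we will conduct preliminary subgroup analyses by race and treatment type". It is labelled Aim 4. Section 2.3 has no Aim 4, so the link to Exploratory Aim 1 is inferred from the content. The Aim 2 model that it borrows is an ANCOVA for post-intervention FFS with "covariates: FFS at baseline and arm".

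Section 11.2 adds analysis as randomized, a two-sided significance level of 0.15 for study hypotheses, and missing-data rules. Neither section mentions an interaction term, a difference between subgroup effects, or a CI for one.

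**The concern.** Whether an effect differs between groups is a question about one quantity: the arm effect in one subgroup minus the arm effect in the other. An ANCOVA with arm and baseline, repeated within each subgroup, gives two arm effects, each with its own uncertainty. It does not give their difference or the uncertainty of that difference. As written, then, the planned output stops short of the question in three sections.

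Race is built into this design. AA/B subjects are oversampled, race is a stratification factor, and the data are meant to support a later trial focused on AA/B survivors (section 1.5). Section 11.1 also says that the efficacy estimates will inform that trial's design. With about 4 to 6 AA/B subjects per arm, two subgroup estimates can look quite different by chance. A reader given no CI for the difference cannot tell how little that means.

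**Working it through.** **Inputs.** From section 11.1: 20 per arm with at least 6 AA/B, a 70% completion target giving 14 evaluable per arm, an effect of 0.66 SD, a pre-post correlation of 0.5 and 70% power. From section 11.2: two-sided alpha 0.15. From the enrollment table in section 3: 12 AA/B, 26 White and 2 Asian subjects.

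**Assumptions.** Race groups split evenly between arms, and retention is equal across them. AA/B per arm is then 6 at full retention and 0.70 × 6 = 4.2, about 4, at 70%. White per arm is 13, and 0.70 × 13 = 9.1, about 9. All non-AA/B per arm is 14, and 0.70 × 14 = 9.8, about 10.

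**Step 1: the plan's own figure.** The ANCOVA residual SD is √(1 − 0.5²) = 0.866. The standard error (SE) of the arm effect is 0.866 × √(2/14) = 0.327. The noncentrality is 0.66/0.327 = 2.02 on 28 − 3 = 25 df. Power is 70.4%, which matches the stated 70%. That figure covers the overall arm effect only.

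**Step 2: the contrast.** With a and b evaluable subjects per arm in the two subgroups:

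SE = 0.866 × √(2/a + 2/b), df = 2(a + b) − 5

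The 5 parameters are the intercept, baseline, arm, factor and arm by factor. For AA/B vs White at 70% retention, SE = 0.866 × √(0.500 + 0.222) = 0.736 on 21 df. The 85% half-width is 1.494 × 0.736 = 1.10. The plan sets no CI level for this contrast; 85% is used here to match alpha 0.15.

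| Race contrast | a / b per arm | SE (SD units) | 85% half-width | Power at 0.66 SD | Difference with 70% power |
|---|---|---|---|---|---|
| AA/B vs White, full retention | 6 / 13 | 0.604 | 0.89 | 36% | 1.21 |
| AA/B vs White, 70% retention | 4 / 9 | 0.736 | 1.10 | 30% | 1.48 |
| AA/B vs all others, full retention | 6 / 14 | 0.598 | 0.88 | 37% | 1.19 |
| AA/B vs all others, 70% retention | 4 / 10 | 0.725 | 1.08 | 30% | 1.46 |

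The AA/B vs White rows leave the 2 planned Asian subjects out of the contrast.

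**Step 3: why the stated power does not carry over.** At 4 and 10 per arm, the variance of the contrast relative to the overall effect is (2/4 + 2/10)/(2/14) = 0.700/0.143 = 4.9.

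**Step 4: treatment type.** The documents give no split. Over assumed splits at 14 evaluable per arm, SE runs from 0.655 (7 and 7, the best case) to 0.935 (2 and 12). The 85% half-width runs from 0.98 to 1.489 × 0.935 = 1.39.

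**The case against.** The strongest reply is that this is an exploratory aim with an analysis called preliminary. The phrase about similar analyses does not exclude an interaction term, and anyone can subtract one subgroup estimate from the other. Fitting one model also buys little precision: a difference built from two separate ANCOVAs has an 85% half-width of about 1.14 SD against 1.08 (4 and 10 per arm), and 0.90 against 0.88 (6 and 14). All of this stands, and it is why the point is minor. It does not close the gap, because the plan still never says that the difference and its CI will be reported.

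Three stronger readings are tempting, and the documents support none of them.

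- A reader might infer that a difference will be declared when one subgroup reaches p < 0.15 and the other does not. With no effect in either group that pattern would occur 2 × 0.15 × 0.85 = 25.5% of the time. But the plan contains no such rule, and the overall hypothesis in section 2.1 includes no race or treatment-type difference. The figure is not evidence against the plan.
- A reader might infer two conflicting race contrasts. Only Exploratory Aim 1 defines a contrast, AA/B vs White. The grouping of Black vs other in section 5.6 defines randomization strata, which need not match. What remains is that section 11.1 says only that the analysis is by race and leaves the 2 other-race subjects unplaced.
- A reader might infer that the later trial's AA/B focus hangs on this result. That focus is already planned and rests on frailty burden and under-representation. Some influence through the efficacy estimates is possible, but no route is spelled out.

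**Conclusion.** The point holds in a limited form. The stated question is a difference in effects, the stated analysis is subgroup results, and the contrast with its CI is not specified. No figure in the plan is wrong; the 70% power reproduces. Low power for the contrast is not itself a fault in an exploratory aim.

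The race contrast would carry an SE of about 0.60 to 0.74 SD and an 85% CI of about ±0.9 to 1.1 SD, with power of about 30% to 37% for a 0.66 SD difference. These figures assume the planned race counts, even splits between arms, equal retention and a pre-post correlation of 0.5. The treatment-type figures rest on assumed splits. Severity is low, and no main conclusion changes.

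**What to change.** In section 11.1, tie the Aim 4 sentence to Exploratory Aim 1 and specify the following for that aim's frailty and TNF-alpha related outcomes:

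- Start from the ANCOVA with arm and the baseline value of the outcome. Add race and arm by race. In a second model, add treatment type and arm by treatment type instead.
- Report the difference in arm effect between subgroups with its CI, state the CI level, and take the subgroup effects from the same model.
- Use the aim's AA/B vs White definition. Say whether the other-race subjects (2 planned) form a third race level or are left out of that contrast.
- Label the results exploratory and unadjusted for multiplicity, and state that no difference will be inferred from separate subgroup p-values.

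The cost is a few sentences and, for a two-level factor, two extra terms per model. No new data are needed, and both factors are already stratified on. The downside is that the race contrast will be visibly imprecise, and the trial stays uninformative about all but very large differences in effect.
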